3.3.3 Exploratory

- Mean trough concentration of GT0918 and its relevant metabolite GT0955 on Days 1, 3, 7 and 14
- To explore relationships between GT0918 and/or GT0955 exposure and selected efficacy and safety endpoints and/or biomarkers
- Screening for novel mutants in subjects who do not respond to GT0918
 - Genotype of SARS-CoV-2 viral isolates
- The association between changes in disease related biomarkers with clinical endpoints

4 STATISTICAL METHODS

4.1 Data Quality Assurance

All tables, figures and data listings to be included in the report will be independently checked for consistency, integrity and in accordance with standard Parexel procedures.

4.2 General Presentation Considerations

Baseline: the last available pre-treatment assessment, unless otherwise specified.

For subjects who are screened, randomized, and undertake the first treatment on the same date, the self-reported symptom questionnaire and ordinal scale at Day 1 visit will be flagged as baseline if baseline assessment is missing.

End of Study (EOS): all required phases of the study including the last scheduled procedure shown in the SoA have been completed.

A subject is considered to have completed the study if he has completed all required phases of the study including the last scheduled procedure shown in the Schedule of Activities (SoA).

The end of the study is defined as the date of last scheduled procedure shown in the SoA for the last enrolled subject or last ongoing subject in the study, whichever comes later.

Study Day will be calculated relative to the date of dose administration i.e. Study Day = Assessment Date - First Dose Date + 1, if Assessment Date is on or after First Dose Date. Assessment Date - First Dose Date, if Assessment Date is before First Dose Date.

If more than one laboratory value is available for a given study day, the last valid observation will be used in summaries, unless otherwise stated. If it is not possible to determine which is the last measurement due to missing times, then the average of all measurements for that study day will be used as the value for that study day. All observations will be presented in listings.

For subjects with duplicate self-reported symptom questionnaire or ordinal scale on the same day for the same visit, the record with the worst total score for questions 1 through 14 will be used for summary purpose. All records will be listed.

Continuous data will be summarized in terms of the mean, standard deviation (SD), median, minimum, maximum, and number of observations, unless otherwise stated. Continuous data that are expected to be skewed will be presented in terms of the maximum, upper quartile, median, lower quartile, minimum and number of observations. The minimum and maximum will be reported to the same number of decimal places as the raw data recorded in the database. The mean, median, lower quartile and upper quartile will be reported to one more decimal place than the raw data recorded in the database. The SD will be reported to two more decimal places than the raw data recorded in the database. In general, the maximum number of decimal places reported shall be four for any summary statistic.

Categorical data will be summarized in terms of the number of subjects providing data at the relevant time point (n), frequency counts and percentages. Any planned collapsing of categories will be detailed in the SAP text and the data displays.

Percentages will be presented to one decimal place. Percentages will not be presented for zero counts. Percentages will be calculated using n as the denominator. If sample sizes are small, the data displays will show the percentages, but any textual report will describe frequencies only.

Changes from baseline in categorical data will be summarized using shift tables where appropriate.

P-values greater than or equal to 0.0001, in general, will be presented to four decimal places. P-values less than 0.0001 will be presented as “<0.0001” and p-values greater than 0.9999 will be presented as “>0.9999”.

Confidence intervals will be presented to one more decimal place than the raw data.

Analysis Visit Window:

For unscheduled visits, analysis visit windows will be applied as in [Table](#) below. Analysis visit windows are only used for by visit summaries, not for time to event calculation which will be based on actual date of data collected.

Table 1 Analysis Visit Window for Unscheduled Visits of blood samples

Mapped to	Visit Window
Screening	[Day -1, Day 1]
Day 3	[Day 2, Day 4]
Day 7	[Day 6, Day 8]
Day 14	[Day 13, Day 15]
Day 28	[Day 26, Day 30]
Day 42	[Day 40, Day 44]

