### 7.2.1.2 NIAID Ordinal Scale

The National Institute of Allergy and Infectious Diseases (NIAID) Ordinal Scale will be assessed by the site daily beginning on Day 1 through Day 28 using AE and Questionnaire data. NIAID Ordinal Scale outcomes will be analyzed on Day 7, Day 14 and Day 28.

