#### NIAID Score Description

The NIAID scoring scale will be assessed daily and defined as the lowest score achieved for that day.

The scoring is based on the clinical status of the patient as described below.

1. Death
2. Hospitalized, on invasive mechanical ventilation or extracorporeal membrane oxygenation (ECMO)
3. Hospitalized, on non-invasive ventilation or high flow oxygen devices
4. Hospitalized, requiring supplemental oxygen
5. Hospitalized, not requiring supplemental oxygen - requiring ongoing medical care (COVID-19-related or other medical conditions preventing hospital discharge)
6. Hospitalized, not requiring supplemental oxygen - no longer requires ongoing medical care
7. Not hospitalized, limitation on activities and/or requiring home oxygen
8. Not hospitalized, no limitations on activities

The subjects' following conditions will be recorded in the CRF and include limitation on activities due to COVID-19:

- Ongoing hospital medical care
- Supplemental oxygen
- Non-invasive ventilation or a high flow oxygen device
- Mechanical ventilation
- ECMO

Subjects will also complete 3 questions about NAIDS as following in the patient questionnaire:

- Home oxygen
- Limited activities
- Hospitalization

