### **7.2.1.3 Symptom improvement and resolution**

Subjects will rate their overall clinical status and severity of symptoms associated with COVID-19 by a daily questionnaire. This questionnaire is for outpatients only.

Subjects will complete 3 questions about their overall clinical status daily, including

- Severity of symptoms
- General physical health, and
- Change in overall health including activity limitation, home oxygen, hospitalization, etc.

The questionnaire contains these symptoms

- Cough
- Shortness of breath
- Feeling feverish
- Fatigue
- Body aches and pain
- Sore throat
- Chills
- Headache
- Nausea
- Vomiting
- Diarrhea
- Changes in taste and smell.

Each symptom will be scored daily by the subject as experienced during the past 24 hours.

Detailed list of symptoms and rating score guideline is document per Appendix 5.

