----------------------------------	----------------------------------	----------------------------------	---------------------------------------

3. Have you returned to your usual physical health (before your COVID-19 illness) (check one)?

Yes 	No 
---------------------------------	--------------------------------

4. Have you returned to your usual activities (before your COVID-19 illness) (check one)?

Yes 	No 
--	--------------------------------

NIAID Daily Questions

1. In the past 24 hours, have you been hospitalized?

Yes 	No 
---------------------------------	---

2. In the past 24 hours, have you required home oxygen?

Yes 	No 
---------------------------------	--------------------------------

3. In the past 24 hours, have you had any limitation on your activities?

Yes 	No 
---------------------------------	--------------------------------

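### SAP 4.2 picks between duplicate same-day NIAID records by a symptom total that contains no NIAID item, so it can keep a better status than the protocol's lowest-of-the-day score

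*SAP*

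**What the plan says.** The duplicate rule is in SAP 4.2, General Presentation Considerations. Its scope is both instruments: "duplicate self-reported symptom questionnaire or ordinal scale on the same day for the same visit, the record with the worst total score". Its selection key is a single one: "the record with the worst total score for questions 1 through 14 will be used for summary purpose. All records will be listed".

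Protocol 7.2.1.2, under NIAID Score Description, fixes the daily value differently: "The NIAID scoring scale will be assessed daily and defined as the lowest score achieved for that day". Level 1 is death and level 8 is not hospitalized with no limitation, so lowest means worst. The same section says that the score "will be assessed by the site daily beginning on Day 1 through Day 28 using AE and Questionnaire data".

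The items that separate the NIAID levels for outpatients are not among questions 1 to 14. SAP Appendix 6.4 puts them in a block of their own, the NIAID Daily Questions, which begins "In the past 24 hours, have you been hospitalized" and goes on to home oxygen and activity limitation.

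Protocol 10.1 gives the SAP precedence where the two documents differ. The SAP lists the eight NIAID levels in sections 3.3.2 and 6.2 but nowhere repeats the lowest-of-the-day definition. Its section on changes from the protocol, 4.10.1.1.3, deals only with missing primary-endpoint data.

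**The concern.** A record of clinical status is being chosen on a variable that does not measure clinical status. A subject can report milder symptoms in one entry and still have the worse NIAID level in it, for example after starting home oxygen or limiting activities. The SAP rule then discards the entry that the protocol says defines the day.

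At stake is a listed secondary endpoint. SAP 4.10.3 uses the daily NIAID value for the percentage at each level, the ordinal GEE model and the proportion worsening from baseline, at Days 3, 7, 14 and 28. Because the SAP takes precedence and is silent on the protocol's definition, a programmer following it would implement the symptom-total key for NIAID as well. No reason is given for departing from the protocol, so this reads as an oversight from writing one sentence for two instruments.

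**Working it through.** The plan states no figure on this point, so there is nothing to reproduce. The check applies each rule to pairs of records from the same day and visit.

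**Inputs**
- SAP rule (SAP 4.2): keep the record with the highest total of questions 1 to 14, and report the NIAID score on that record.
- Protocol rule (protocol 7.2.1.2): report the lowest NIAID score of the day.
- Range of the total (SAP 6.4): questions 1 to 12 score 0 to 3 and questions 13 and 14 score 0 to 2, so the maximum is 12 × 3 + 2 × 2 = 40. None of the 40 points comes from a NIAID item.

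**Constructed pairs** (not trial data), written as (symptom total, NIAID score)

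| Record A | Record B | SAP keeps | Protocol gives | Agree? |
|---|---|---|---|---|
| (12, 8) | (9, 7) | 8 | 7 | no |
| (14, 8) | (11, 7) | 8 | 7 | no |
| (14, 7) | (11, 4) | 7 | 4 | no |
| (11, 7) | (14, 4) | 4 | 4 | yes |
| (12, 7) | (11, 7) | 7 | 7 | yes |
| (14, 7) | (none, 5) | not defined | 5 | cannot be said |

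**When they differ.** Two conditions must both hold: the duplicates carry different NIAID scores, and the record with the worse status has the lower symptom total. Home oxygen and activity limitation share level 7, so new home oxygen is lost only against a record scored 8.

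**Direction.** The SAP reports the score of one record in the set, while the protocol reports the minimum of the set. A member of a set is never below its minimum, so the SAP value is always equal to or better than the protocol value. On a post-baseline day every discrepancy therefore favours the subject's apparent status. At baseline the effect on the worsening analysis reverses: a baseline status recorded as too good makes later worsening look more frequent.

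**Missing total.** Protocol 7.2.1.3 says of the symptom questionnaire: "This questionnaire is for outpatients only". A NIAID record from another source may thus have no total. The SAP does not say whether such a record loses, wins or is handled in some other way.

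**The case against.** The strongest reply is that the two rules may do different jobs. The protocol says how the site forms one score per day; the SAP says which repeated entry to use. If the site builds an evening admission into a single daily score, no duplicate arises and the SAP rule never acts. Inpatient status also has its own line in the Schedule of Activities. This limits the reach of the point but does not remove it, because the SAP sentence expressly provides for duplicate ordinal-scale records and gives them the wrong key.

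The consequences are also contained. Protocol 7.2.1.1 records hospitalization, oxygen and death separately in the eCRF, so the primary endpoint should not move. Hospitalization and oxygen use have their own summaries, all duplicate records are listed, and the NIAID model is run only if the data support it. All of this stands.

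Three stronger readings are tempting and should not be drawn.

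- *Inpatient statuses are systematically replaced by outpatient ones.* This needs the hospital record to be a duplicate for the same visit, and a record without a symptom total to be ineligible. The documents establish neither.
- *One or two errors, a large share of the severe categories.* Taking the SAP's under-two-percent hospitalization figure at its ceiling, the planned 668 subjects, and admissions spread evenly over 28 days gives 668 × 0.02 × 4/28 = 1.9. That counts admissions falling on an analysis day. An error also needs a discordant duplicate with a lower symptom total on the worse record, so this is not a count of errors. Subjects already in hospital on an analysis day also fill the severe levels, so no share can be derived.
- *The key is equally wrong for the symptom endpoints.* Those use questions 3 to 9, questions 1 to 9 as sensitivity, or the overall item. Choosing one whole questionnaire by its full total is a defensible way to keep a day's answers together, and re-keying to questions 3 to 9 would not match the sensitivity analyses. That is a matter of preference.

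**Conclusion.** The point holds in a limited form. For duplicate NIAID records on the same day and visit, SAP 4.2 uses a selection key that conflicts with protocol 7.2.1.2, and when the worse status has the lower symptom total it keeps the better one. Where a record has no total, the rule is incomplete.

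The shift can be one level, as in 8 for 7, or more, as in 7 for 4 in the constructed pair. It can reach the NIAID status percentages, the ordinal GEE and the proportion worsening at the four analysis days. The frequency cannot be computed, since neither document says how many duplicates exist or how many disagree; it is probably small. The conclusion rests on the wording of the two sections and on the SAP's precedence. It does not rest on any assumed event rate. It is a minor defect in a secondary endpoint, worth correcting because the conflict is plain and the repair is nearly free.

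**What to change.** In SAP 4.2, limit the rule based on questions 1 to 14 to duplicate symptom questionnaires, and add: *For duplicate NIAID ordinal-scale records on the same day, the lowest (worst) score will be used, as defined in protocol 7.2.1.2.* This restores the protocol definition and also settles the case where a record has no symptom total, since the NIAID choice no longer depends on one.

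The cost is one sentence in the SAP and a small change to the NIAID derivation. No new data are needed, and the symptom endpoints and the primary analysis stay as they are.

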4.3 Software

All report outputs will be produced using SAS® version 9.4 [1] or a later version in a secure and validated environment.

4.4 Study Subjects

4.4.1 Disposition of Subjects

A clear accounting of the disposition of all subjects who enter the study will be provided, from screening to study completion. The disposition summary will include:

- number of patients screened
- number of patients screened failure
- number of patients in each analysis sets
- number of patients completed treatment
- number and reason of patients withdrew early from the treatment
- number of patients completed post-treatment
- number of patients withdrew early from the post-treatment
- number of patients completed study
- number and reason of patients withdrew early from the study

By-subject listings of eligibility details, randomization details, visit dates and withdrawal/study completion details (including reason for discontinuation and duration of treatment prior to discontinuation) will be provided. Disposition data will be listed and summarized for all enrolled population.

4.4.2 Protocol Deviations

Protocol deviations will be identified and classified into major or minor. Major protocol deviations are defined as those deviations from the protocol likely to have an impact on the perceived efficacy and/or safety of study treatments.

Major protocol deviations and any action to be taken regarding the exclusion of subjects or affected data from specific analyses are defined in the project-specific Protocol Deviation Specification. The final determination of major protocol deviations and the exclusion of patients from any of the analysis populations will be made prior to database lock.

A summary of the number and percentage of subjects with a major protocol deviation will be provided by treatment group and type of deviations using ITT set. A by-subject listing will be provided for all reported protocol deviations.

4.5 Analysis Sets

The Intent-to-Treat Analysis Set (ITT) includes all randomized subjects.

The Modified Intent-to-Treat Analysis Set (mITT) includes all randomized subjects who have received at least one dose of study medication. The primary efficacy analysis will be conducted on the mITT Analysis Set.

The Safety Analysis Set (SS) includes all subjects with at least one dose of study medication and will be analyzed as treated. The disposition, study summary, and safety analysis will be conducted on Safety Analysis Set.

The Per-Protocol Analysis Set (PP) includes all mITT subjects without major protocol violations which will be defined under classification specification prior to unblinding of the study treatment code.

The Pharmacokinetic Analyses (PK) will be conducted on data from at least 200 subjects who receive intervention and have evaluable PK.

4.6 Demographic and Other Baseline Characteristics

Demographic and other baseline characteristics will be summarized by treatment group using the ITT set. The summaries provided will include the following:

- Demography
 - Age in years, age group (<50 years; \geq 50 years), age group (<60 years; \geq 60 years), and age group (<65 years; \geq 65 years)
 - Sex
 - Race
 - Ethnicity
 - Baseline height
 - Baseline weight
 - Baseline BMI
 - Baseline BMI categories as below
 - Underweight (<18.5)
 - Normal (\geq 18.5 and <25.0)
 - Overweight (\geq 25.0 and <30.0)
 - Obesity (\geq 30.0)
 - Obesity Class 1 (\geq 30.0 and < 35.0)
 - Obesity Class 2 (\geq 35.0 and < 40.0)
 - Obesity Class 3 (\geq 40.0)
- Other Baseline Characteristics
 - Days from the positive SARS-CoV-2 prior to first dosing and test type
 - Days from onset of COVID-19 symptoms prior to first dosing
 - Prior COVID-19 therapy
 - Number of high-risk medical factors (0; 1-2; \geq 3)
 - High-risk medical status by below categories
 - Age \geq 65 years
 - Cancer
 - Chronic kidney disease
 - Chronic lung diseases
 - Chronic obstructive pulmonary disease
 - Asthma
 - Interstitial lung disease
 - Cystic fibrosis
 - Pulmonary hypertension
 - Dementia or other neurological conditions
 - Dementia

- Other
- Down syndrome
- Heart conditions
 - Heart failure
 - Coronary Artery Disease
 - Cardiomyopathies
 - Hypertension
- Immunocompromised state (weakened immune system) from solid organ transplant
- Liver disease
- Overweight and Obesity (BMI ≥ 25 kg/m²)
 - Overweight (BMI ≥ 25.0 kg/m² and < 30.0 kg/m²)
 - Obesity (BMI ≥ 30.0 kg/m² and < 40.0 kg/m²)
 - Sever Obesity (BMI ≥ 40.0 kg/m²)
- Sickle cell disease or Thalassemia
 - Sickle cell
 - Thalassemia
- Smoking (current or former)
 - Current
 - Former
- Diabetes (type 1 or type 2)
 - Type 1
 - Type 2
- HIV infection
- Solid organ or blood stem cell transplant
 - Solid organ transplant
 - Blood stem cell transplant
- Stroke or cerebrovascular disease, which affects blood flow to the brain
 - Stroke
 - Cerebrovascular disease
- Substance use disorders
- Other

- Medical history will be reported by system organ class (SOC) and preferred term (PT) as coded using the Medical Dictionary for Regulatory Activities (MedDRA) Version 24.0 or higher.
- Medication allergy history will also be reported by SOC and PT separately.
- Baseline patient reported COVID-19 symptom questionnaires will be summarized.

Categorical data will be presented as frequencies and percentages. For continuous data, mean, standard deviation, median, 25th and 75th percentiles, minimum, and maximum will be presented. By-subject listings of demographic data, other baseline characteristics (as summarized above), high-risk medical status, medical history and patient reported COVID-19 symptom questionnaires at baseline will be provided.

4.7 Concomitant Medication

All medications administered within 30 days prior to the first dose of study treatment through 28 days after the last dose of study treatment will be recorded in the concomitant medications. Medications will be coded using Anatomical Therapeutic Chemical (ATC) Classification codes by World Health Organization Drug Dictionary (WHO-DD-March 2021) or latest version. Prior and concomitant medications will be summarized by ATC class level II, and Preferred Term.

Medication start and stop dates will be compared to the date of first dose of study medication to allow medications to be classified as either Prior only, both Prior and Concomitant, or Concomitant only. Medications starting after the completion/withdrawal date will be listed but will not be classified or summarized.

Medications that start and stop prior to the date of first dose of study medication will be classified as Prior only. If a medication starts before the date of first dose of study medication and stops on or after the date of first dose of study medication, then the medication will be classified as both Prior and Concomitant. Medications will be classified as Concomitant only if they have a start date on or after the date of first dose of study medication.

If medication start and/or stop dates are missing or partial, the dates will be compared as far as possible with the date of first dose of study medication. Medications will be assumed to be Concomitant only, unless there is clear evidence (through comparison of partial dates) to suggest that the medication started prior to the first dose of study medication. If there is clear evidence to suggest that the medication started prior to the first dose of study medication, the medication will be assumed to be both Prior and Concomitant, unless there is clear evidence to suggest that the medication stopped prior to the first dose of study medication. If there is clear evidence to suggest that the medication stopped prior to the first dose of study medication, the medication will be assumed to be Prior only.

In the summary of prior and concomitant medications, each subject will be counted once within each unique term. For example, if a subject takes amoxycillin on 2 separate occasions, the subject is counted only once under the corresponding ATC class.

Summaries and by-subject listings will be given for Safety set. The summary will group the medication by Prior only, Prior and Concomitant and Concomitant only.

Standard of Care

Subjects should be treated according to standard of care.

Remdesivir may be initiated as standard of care for subjects hospitalized with severe disease.

All medications administered as the local standard of care per written policies or guidelines (that is, not just an individual clinician decision) such as lopinavir/ritonavir, chloroquine, hydroxychloroquine or other investigational agents. will be summarized separately.

